## 7 Appendix 1: Definitions from the protocol

**Adjunctive Compression:** Compression methods (including sand bags, compression bandages, and light manual pressure) for controlling cutaneous or subcutaneous oozing.

**Adverse Device Effect (ADE):** Adverse event (see definition below) resulting from insufficient or inadequate instructions for use, deployment, implantation, installation, or operation, or any malfunction of the investigational medical device. This definition includes any event resulting from use error or from intentional misuse of the investigational medical device.

**Adverse Event (AE):** Any untoward medical occurrence, unintended disease or injury, or untoward clinical signs (including abnormal laboratory findings) in subjects, users or other persons, whether or not related to the medical device. This definition includes events related to the procedures involved. For users or other persons, this definition is restricted to events related to devices.

**Cachexia:** Defined as very thin, or body mass index <20 kg/m^2.

**Device Deficiency:** Inadequacy of a medical device with respect to its identity, quality, durability, reliability, safety or performance; includes device malfunctions, use errors and inadequate labeling

**Eccymosis:** An area of subcutaneous discoloration caused by the extravasation of blood into the subcutaneous tissue not associated with a definable, palpable subcutaneous mass.

**Hematoma:** An expanding or non-expanding subcutaneous mass of blood greater than 2 cm in its longest axis, confirmed by ultrasound.

**Hemostasis Success:** Hemostasis at the puncture site within 10 minutes of removing the MANTA sheath without need for manual or mechanical compression and without later rebleeding (trivial or subcutaneous oozing will not be considered bleeding; light finger pressure to control subcutaneous oozing will not be considered manual compression).

**Major and Minor Access Site Related Complications (as described below):** within 30 days of procedure. Adapted from the VARC-2 Clinical Guidelines [3]

**Major femoral vascular complications:** Composite endpoint that includes any of the following adverse events:

- Femoral access site or access-related vascular injury (dissection, stenosis, perforation, rupture, arterio-venous fistula, pseudoaneurysm, hematoma, irreversible nerve injury, compartment syndrome, percutaneous closure device failure) leading to death, lifethreatening or major bleeding; OR,
- Downstream distal embolization (lower extremities) requiring surgery or resulting in amputation; OR,
- The use of unplanned endovascular or surgical intervention associated with death, major femoral bleeding; OR,
- Any new ipsilateral lower extremity ischemia documented by patient symptoms, physical exam, and/or decreased or absent blood flow on lower extremity angiogram; OR,
- Surgery for femoral access site-related nerve injury; OR,

- Permanent femoral access site-related nerve injury (lasting >30 days).

Minor femoral vascular complications: Composite endpoint that includes any of the following adverse events:

- Femoral access site or access-related vascular injury (dissection, stenosis, perforation, rupture, arterio-venous fistula, pseudoaneuysms, hematomas, percutaneous closure device failure) not leading to death, life-threatening or major bleeding; OR,
- Downstream distal embolization (lower extremities) treated with embolectomy and/or thrombectomy and not resulting in amputation; OR,
- Any unplanned endovascular stenting or unplanned surgical intervention not meeting the criteria for a major vascular complication; OR,
- Vascular repair or the need for vascular repair (via surgery, ultrasoundguided compression, transcatheter embolization, or stent-graft); OR,
- Percutaneous closure device failure\*; OR,
- Any other adverse event that is definitely or probably device-related or access-site related.

\*Failure of a closure device to achieve hemostasis at the arteriotomy site leading to alternative treatment (other than manual compression or adjunctive endovascular ballooning)

Morbid Obesity: Defined by the position of the access needle whereby less than one third of the access needle is above the skin line indicating the subject is morbidly obese, or body mass index >40 (weight in kg divided by square of height in meters).

Nerve Injury: Any ipsilateral transient or permanent sensory or motor neurologic deficit of the femoral nerve, or anterior or lateral cutaneous femoral nerve, or evidence of sacral plexus injury from documented retroperitoneal bleeding, as determined by a neurologist.

Oozing: Bleeding of a cutaneous or subcutaneous origin that can be controlled with the application of light compression methods (sand bags, compression bandages, or light manual pressure) and which do not apply sufficient compression to control arterial bleeding. Light manual compression may be substituted by light compression from a mechanical device.

Pre-existing Hematoma: An expanding or non-expanding subcutaneous mass of blood present prior to the start of the access site closure.

Serious Adverse Device Effect (SADE): An Adverse Device Effect that has resulted in any of the consequences characteristic of a Serious Adverse Event.

Serious Adverse Event (SAE): An SAE is an Adverse Event that:

- Lead to death
- Lead to life threatening or major bleeding - requiring transfusion of two or more whole blood/RBC
- Lead to a permanent injury or permanent impairment to a body structure or a body function
- In patient or prolonged hospitalization
- Medical or surgical intervention to prevent life-threatening illness
- Lead to visceral ischemia

Note: For this study, planned hospitalization for a pre-existing condition, or a procedure required by this protocol, without serious deterioration in health, is not considered a serious adverse event.

Severe Peripheral Vascular Disease: Any of the following:

- Severe claudication when ambulating <30 meters
- Weak or absent pulses in the affected limb
- Known stenosis >50% in the iliac or femoral artery on the affected side
- Prior vascular bypass surgery involving the affected femoral artery

Significant Calcium: Visible calcium on fluoroscopy or CTA. Document calcium on MFACS scale (MFACS is not exclusionary), Manta Femoral Artery Calcification Score (MFACS)

- 0 - No calcification
- 1 - Minor calcification
- 2 – Moderate anterior and posterior wall calcification
- 3 – Significant posterior wall calcification
- 4 – Significant anterior wall calcification
- 5 – Circumferential wall calcification

Stable Access Site Status: Defined as ability to walk at least 6 meters, freedom from orthostatic hypotension [defined as stable blood pressure and heart rate after ambulating], ability to void and a stable access site without bleeding or expansion of a prior hematoma.

Time to Ambulation: The elapsed time between post-MANTA deployment (time suture cut away from body) and when ambulation is achieved (patient standing and walking at least 6 meters without re-bleeding).

Time to Hemostasis: The elapsed time between MANTA deployment (withdrawal of sheath from artery) and first observed and confirmed arterial hemostasis (no or minimal subcutaneous oozing and the absence of expanding or developing hematoma).

Total MANTA Procedure Time: The elapsed time between pre-MANTA deployment (exchange of procedure sheath with MANTA sheath) to post-MANTA deployment (time suture cut away from body).

Procedure Success: A patient will be considered a Procedure Success if he/she has no Major Complications (as defined above) within 30 days post procedure.

Unanticipated Serious Adverse Device Effect (USADE): A Serious Adverse Device Effect, which by its nature, incidence, severity or outcome has not been identified in the current version of the risk analysis report. Note: An anticipated serious adverse device effect is a serious adverse device effect which by its nature, incidence, severity or outcome has been identified in the risk analysis report.

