	
or absent blood flow on lower extremity angiogram; OR, surgery for femoral access site-related nerve injury; OR, permanent femoral access site-related nerve injury.
 
Minor femoral vascular complications:
 
Access site or access-related vascular injury (dissection, stenosis, perforation, rupture, arterio-venous fistula, pseudoaneuysms, hematomas, percutaneous closure device failure) not leading to death, life-threatening or major bleeding; OR, downstream distal embolization (lower extremities) treated with embolectomy and/or thrombectomy and not resulting in amputation; OR, any unplanned endovascular stenting or unplanned surgical intervention not meeting the criteria for a major vascular complication; OR, vascular repair or the need for vascular repair (via surgery, ultrasound-guided compression, transcatheter embolization, or stent-graft); OR, percutaneous closure device failure*.
 
*Failure of a closure device to achieve hemostasis at the arteriotomy site leading to alternative treatment (other than manual compression or adjunctive endovascular ballooning).
 
2. Time to Hemostasis: The elapsed time between MANTA deployment (withdrawal of sheath from artery) and first observed and confirmed arterial hemostasis (no or minimal subcutaneous oozing and the absence of expanding or developing hematoma).

Clinical Visits/Testing	
 ▪ Baseline evaluation: Informed consent, history and physical, CT Angiographic Scan ▪ Index Procedure: Adverse Events ▪ Pre-MANTA Closure Procedure: Target Femoral Access Site Visual Assessment ▪ MANTA Closure Procedure: ACT/Systolic Blood Pressure ▪ Post-MANTA Closure Procedure: Femoral Angiography, Target Femoral Access Site Visual Assessment, Time to Hemostasis, Adverse Events ▪ Post procedure: Target Femoral Access Site Visual Assessment, Adverse Events ▪ Discharge: Target Femoral Access Site Visual Assessment, Time to Ambulation, Adverse Events ▪ 30D (+/- 7 days): Clinical Exam, Target Femoral Access Site Visual Assessment, Adverse Events 
 • 30 Day Follow-Up may be done via phone if not SOC/ per site SOC timing (6 weeks) ▪ 12M (+/- 30 days): Clinical Exam, Target Femoral Access Site Visual Assessment, Adverse Events (subset only)

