Adverse Event (AE): Any untoward medical occurrence, unintended disease or injury, or untoward clinical signs (including abnormal laboratory findings) in subjects, users or other persons, whether or not related to the medical device. For the purpose of this protocol, AEs to be recorded include AEs associated with the MANTA device, AEs related to the non-MANTA access site, and additional outcomes either associated or not associated with the MANTA device. This definition includes events related to the procedures involved. For users or other persons, this definition is restricted to events related to devices. For the subjects followed up at 12M, only AEs related to the MANTA access site or the ipsilateral leg will be collected.

Cachexia: Defined as very thin, or body mass index $<20 \text{ kg/m}^2$.

Device Deficiency: Inadequacy of a medical device with respect to its identity, quality, durability, reliability, safety or performance; includes device malfunctions, use errors and inadequate labeling

Ecchymosis: An area of subcutaneous discoloration caused by the extravasation of blood into the subcutaneous tissue not associated with a definable, palpable subcutaneous mass.

Hematoma: An expanding or non-expanding subcutaneous mass of blood greater than 2 cm in its longest axis, confirmed by ultrasound.

Hemostasis Success: Hemostasis at the puncture site within 10 minutes of removing the MANTA sheath without need for manual or mechanical compression and without later re-bleeding (trivial or subcutaneous oozing will not be considered bleeding; light finger pressure to control subcutaneous oozing will not be considered manual compression).

Major and Minor Access Site Related Complications (as described below): within 30 days of procedure. Adapted from the VARC-2 Clinical Guidelines [3]

Major femoral vascular complications: Composite endpoint that includes any of the following adverse events:

- Femoral access site or access-related vascular injury (dissection, stenosis, perforation, rupture, arterio-venous fistula, pseudoaneurysm, hematoma, irreversible nerve injury, compartment syndrome, percutaneous closure device failure) leading to death, life-threatening or major bleeding; OR,
- Downstream distal embolization (lower extremities) requiring surgery or resulting in amputation; OR,
- The use of unplanned endovascular or surgical intervention associated with death, major femoral bleeding; OR,

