Procedure Success: A patient will be considered a Procedure Success if he/she has no Major Complications (as defined above).

Unanticipated Serious Adverse Device Effect (USADE): A Serious Adverse Device Effect, which by its nature, incidence, severity or outcome has not been identified in the current version of the risk analysis report. Note: An anticipated serious adverse device effect is a serious adverse device effect which by its nature, incidence, severity or outcome has been identified in the risk analysis report.

5. Study Objectives

The following Performance Endpoints will be evaluated for the MANTA device (definitions are provided in Section 4):

1. Time to Hemostasis (Primary)

The following Safety Endpoints will be evaluated for the MANTA device (definitions are provided in Section):

1. The percentage of patients with one or more VARC-2 Major femoral vascular complications within 30±7 days following procedure (Primary)
2. The percentage of patients with one or more VARC-2 Minor femoral vascular complications within 30±7 days following procedure (Secondary)

6. Study Design

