7.8 Sponsor Representatives

Trained Sponsor personnel may perform certain study activities to ensure compliance to the clinical protocol and may provide technical expertise. Monitoring may be performed by Essential Medical and/or authorized designees according to the International Organization for Standardization (ISO) 14155 and MEDDEV guidelines for post market studies; and applicable Essential Medical standard operating procedures and work instructions. Qualified monitors will ensure investigators comply with this clinical protocol and ISO 14155 and MEDDEV post market requirements.

To ensure study personnel accept, understand and complete their assigned responsibilities, monitors, or field clinical personnel may perform periodic site visits during the course of the study. These actions will help to ensure the continued acceptability of the facilities, compliance to the clinical protocol and relevant regulations, and the maintenance of complete records.

Monitoring will include review and resolution of missing or inconsistent results and source document verification (i.e. comparison of submitted study results to original reports) to assure the accuracy of the reported data.

8. Statistical Methods

8.1. *Study Hypothesis*

This is a single arm study, and no formal hypothesis will be tested.

8.2. *Sample Size Considerations*

Up to 500 subjects are considered a meaningful sample size to assess real-world use of the MANTA device. There is no statistical basis for the sample size.

8.3. *Data Analysis*

8.3.1 *Endpoints*

The following Performance Endpoints will be evaluated for the MANTA device, definitions are provided in Section 4:

1. Time to Hemostasis (Primary)

The following Safety Endpoints will be evaluated for the MANTA device, definitions are provided in Section 4:

1. The percentage of patients with one or more VARC-2 Major femoral vascular complications within 30 ± 7 days following procedure (Primary)
2. The percentage of patients with one or more VARC-2 Minor femoral vascular complications within 30 ± 7 days following procedure (Secondary)

8.3.2 *Final Analysis*

Statistical analysis will consist of descriptive statistics using standard methods, such as mean, standard deviation, minimum/maximum, proportions, counts, etc. Two-sided 95% confidence

intervals will be calculated, when relevant. Comparison to published literature results will be descriptive only; there will be no comparative statistics.

8.4. *Interim Analysis*

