9.5. Reporting of Adverse Events

9.5.1 SAE and AE Reporting to Sponsor

Safety Surveillance within this registry and the safety reporting performed by both the investigator and Sponsor starts from the point of attempted MANTA placement and onward. The safety surveillance and the safety reporting will continue until the last visit has been performed, the subject is deceased. The subject/investigator concludes their participation in the study or the subject/investigator withdraws the subject from the study. All device-related SAEs from the point of attempted MANTA placement and onward will be reported to the Sponsor within 24 hours of the Investigator’s first knowledge of the event. Suspected SAEs also should be reported. Investigators should also report AEs or SAEs that are known to be unrelated to the device on eCRF.

The Investigator will forward information about a device-related SAE promptly and complete the AE and SAE report forms provided by the Sponsor, even if the information is incomplete or it is obvious that more data will be needed to form any conclusions. Additional information regarding the SAE will be recorded on the follow-up SAE form and forwarded to the Sponsor.

All MANTA device-related AEs, and AE’s associated with non-MANTA access sites, and additional outcomes not associated with MANTA device should be reported on the eCRF as soon as practicably possible. Such AEs will be recorded by their final medical diagnosis and not by each separate symptom. All AEs categorized by the Investigator as associated with MANTA leg and categorized by the Investigator as possibly, probably or definitely device-related, will be reviewed by the Clinical Events Committee for a final adjudication. The information for the event will include the date of onset and resolution, the action taken, the intervention/treatment and how the subject recovered with or without sequelae. In case of death, the relationship of death to the MANTA device and/or the study procedure will be well documented. The date on

which subject expired, what attempts were made to treat the event that led to death, the performance and functioning of the device during the event will be noted.

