As the MANTA device is CE-marked, device-related AEs and SAEs will be recorded by the Sponsor as complaints, in accordance with the Sponsor's Quality System. Such complaints will be analyzed to determine if vigilance reporting is required and any required vigilance reports filed with EU competent authorities in accordance with EU medical device vigilance requirements.

9.6 *Device Deficiencies*

The Investigator will record any device deficiencies, as defined in Section 4, in the CRF. A device deficiency has occurred if a device used in the study procedure failed to meet its performance specifications whether due to mechanical failure, malfunction or defects. Device deficiencies also include use errors and inadequate labeling. This applies to:

- devices used in the subject; or
- devices in which the package was opened, but the device was not used on the subject; or
- devices with which at least one insertion attempt was made, but the device did not remain in the subject.

If the device deficiency was associated with an AE, the reporting provisions for AEs, ADEs, SAEs, SADEs and USADEs as outlined in above apply. Any device deficiency that did not lead to an AE but could have led to a SADE, if suitable action had not been taken, if intervention had not been made, or if circumstances had been less fortunate, must be reported to the Sponsor within 24 hours of the event using the CRF. Reporting to the EC and/or Competent Authority will follow EU vigilance requirements. All device deficiencies will be recorded on the CRF. Device deficiencies which could not have led to a SADE must be reported to the Sponsor within 3 business days. All devices alleged to be deficient must be returned to the Sponsor within 5 business days.

9.7. *Clinical Events Committee (CEC)*

An independent Clinical Events Committee (CEC) will be established for this study. The CEC will have at least two members who are qualified to review adverse event data from this study. The CEC will be established and operate according to a charter defined prior to the initiation of the trial. The CEC will review individual adverse events that meet the following criteria:

- AEs that are considered by the investigator to be definitely, probably or possibly device-related and will be adjudicated by CEC parallel to enrollment. Additionally, outcomes not associated with the MANTA device may also be adjudicated by CEC.

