## 5.3 Safety Endpoint 2: VARC-2 Minor Complication

Objective: To quantify the real-world VARC-2 minor femoral vascular complication incidence using the MANTA device.

Endpoint: The percentage of patients with one or more VARC-2 Minor femoral vascular complications (and no major VARC-2 complications) as adapted from VARC-2 definitions within 30 days following procedure.

Minor femoral vascular complication definition:

- Access site or access-related vascular injury (dissection, stenosis, perforation, rupture, arterio-venous fistula, pseudoaneuysms, hematomas, percutaneous closure device failure) not leading to death, life-threatening or major bleeding; OR,
- downstream distal embolization (lower extremities) treated with embolectomy and/or thrombectomy and not resulting in amputation; OR,
- any unplanned endovascular stenting or unplanned surgical intervention not meeting the criteria for a major vascular complication; OR,

- vascular repair or the need for vascular repair (via surgery, ultrasound guided compression, transcatheter embolization, or stent-graft); OR,
- percutaneous closure device failure\*.

\*Failure of a closure device to achieve hemostasis at the arteriotomy site leading to alternative treatment (other than manual compression or adjunctive endovascular ballooning).

Subjects to include: All subjects with a procedure attempt will be included in this analysis.

Statistical analysis (patient based): The number of subjects, percentage of patients and 95% confidence intervals for the percentage of subjects will be calculated at a minimum for subjects experiencing any type of minor complication as previously defined. Additional summaries may include splitting into adverse event type as collected via the case report forms.

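### SAP 5.3 analyses a narrower minor-complication endpoint than Protocol 8.3.1 defines, SAP 3 keeps some qualifying events from adjudication, and one benchmark in SAP Table 2 is unreconciled

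*SAP*

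**What the plan says.** **Element list.** Protocol 8.3.1 states: "The following Safety Endpoints will be evaluated for the MANTA device, definitions are provided in Section 4". Section 4 gives six elements for a minor femoral vascular complication, the sixth being "Any other adverse event that is definitely or probably device-related or access-site related". SAP Appendix 1, which reproduces the protocol's definitions, has the same six. The protocol synopsis has five, its list ending "transcatheter embolization, or stent-graft); OR, percutaneous closure device failure". SAP 5.3 has the same five.

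**Who is counted.** Protocol Section 5 words the endpoint as "one or more VARC-2 Minor femoral vascular complications within 30±7 days following procedure (Secondary", and 8.3.1 does the same; neither mentions major complications. SAP 5.3 counts "The percentage of patients with one or more VARC-2 Minor femoral vascular complications (and no major VARC-2 complications) as adapted from VARC-2 definitions".

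**What reaches the CEC.** Under Protocol 9.5.1, MANTA-leg events "categorized by the Investigator as possibly, probably or definitely device-related, will be reviewed by the Clinical Events Committee for a final adjudication". Protocol 9.7 names "AEs that are considered by the investigator to be definitely, probably or possibly device-related and will be adjudicated by CEC parallel to enrollment". SAP 3 repeats that rule, then lists events that will not be submitted: hematomas below 2 cm or with no size on record, and minor bleeding, when left untreated or handled by compression alone. Its reason is that they satisfy neither VARC-2 nor the protocol's definitions. Protocol Section 4 defines a hematoma as "An expanding or non-expanding subcutaneous mass of blood greater than 2 cm in its longest axis, confirmed by ultrasound". Protocol 9.7 and SAP 3 both base the safety endpoints on adjudicated data.

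**Benchmark.** For the EU pre-market study, Protocol 1.4 reports five minor complications in 5 of 50 subjects (10%), all of them true access-site hematomas. SAP Table 2 shows 0/50 (0%) for the same study. SAP 5 names that study as one of two that MARVEL will at least be compared with.

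**The concern.** SAP Section 1 presents the SAP as adding detail to the protocol. A reader of the final report would therefore take the SAP 5.3 rate to be the protocol's minor-complication endpoint. If SAP 5.3 is followed as written, it is a different quantity, and each difference can only leave the count unchanged or lower it. No passage says which element list governs or discloses a departure.

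The rate also has a stated use. SAP 5 fixes in advance what will be reported when a benchmark rate lies inside MARVEL's 95% confidence interval. With the numerator rule unsettled and one required benchmark given as both 0% and 10%, that statement has no fixed meaning for minor complications.

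**Working it through.** The plan states no design figure for this endpoint, and both documents say that the sample size has no statistical basis, so there is none to reproduce. The one nearby summary figure, the weighted minor rate in SAP Table 3, does reproduce: sum of (N × rate) / sum of N = 30,669.2 / 2,659 = 11.53% (stated 11.5%). The problem lies in the definitions and in Table 2.

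**Step 1. The texts side by side.**

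| Place | Elements | Catch-all | Patients with a major complication |
|---|---|---|---|
| Protocol synopsis | 5 | no | not excluded |
| Protocol Section 4, used by 8.3.1 | 6 | yes | not excluded |
| SAP 5.3 | 5 | no | excluded |
| SAP Appendix 1 | 6 | yes | not excluded |

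The protocol endpoint follows the second row and the SAP analysis the third.

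**Step 2. Direction.** Fix the denominator, the window and the onset dates. Every patient counted by SAP 5.3 has an event in the five-element list, hence in the six-element list, and so is counted by Protocol 8.3.1. The SAP 5.3 patients are a subset, and the rate is equal or lower. Against the synopsis list, the only sources of a difference are the no-major limit and possibly unsized hematomas.

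**Step 3. Withheld events.**
- *Hematoma below 2 cm, or minor bleeding.* The first does not meet the protocol's hematoma definition and the second is not a listed injury. Withholding them matters only under the catch-all. There, an event that is definitely or probably device-related or access-site related does meet a protocol definition, so the reason given in SAP 3 is not correct for it.
- *Hematoma of unrecorded size.* It may exceed 2 cm and so belong to the first element of either list. Withholding it treats a missing measurement as a non-event, although SAP 6 says missing data are not imputed.
- *Conflict with Protocol 9.5.1.* This covers only MANTA-leg events that the investigator rates at least possibly device-related. For these, non-submission means they cannot enter the endpoint.

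**Step 4. Bound on the no-major limit.** Patients removed ≤ patients with a major complication = N × VARC-2 major rate. With N = 500 assumed:
- Table 2, EU study: 500 × 2% = 10 patients (2.0 points)
- Table 2, US pivotal trial: 500 × 4.2% = 21 patients (4.2 points)
- Table 3, lowest MANTA row: 500 × 1.1% = 5.5, so 5 patients
- Table 3, highest MANTA row: 500 × 9.3% = 46.5, so 46 patients

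The minimum is 0. The upper values need every patient with a major complication to have a separate minor one as well. The documents give no figure from which to size the catch-all or the unsized hematomas.

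**Step 5. The EU benchmark.** Exact (Clopper-Pearson) 95% intervals are 3.3% to 21.8% for 5/50 and 0% to 7.1% for 0/50. The no-major rule cannot by itself turn 5 into 0: Protocol 1.4 reports a Major Complication in 3 subjects and Table 2 shows 1 VARC-2 major, so at least 5 − 3 = 2 would remain. Which value is used can matter. At an arbitrary 39/500 (7.8%, exact interval 5.6% to 10.5%), 10% lies inside the interval and 0% outside.

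**The case against.** The strongest reply is that SAP 5.6 already covers much of this. It plans counts and percentages of patients with MANTA-related minor complications without stating a no-major limit, and splits them by definition element. It also lists every event the investigator considered MANTA-related, with treatment, severity and any CEC classification. A reader might infer from SAP 3 that the withheld events disappear from the report. They do not: they stay visible, but outside the 5.3 rate. SAP 5.6 does not amend SAP 5.3, and an event never sent to the CEC has no classification that could place it in a minor-complication count.

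Second, five elements can be defended. The synopsis has them, the endpoint is named after VARC-2, and the catch-all is not confined to vascular events. A reader might infer that the six-element list must be the only main row. The documents do not settle that: Protocol 8.3.1 points to six, the synopsis gives five, and the narrower list may suit comparison with VARC-2 literature better. What stands is that the choice must be stated.

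Third, the withheld set is narrow and matters mostly if the catch-all applies. SAP 3 can also be read as a general rule followed by exceptions. That is fair, but the exceptions rest on an incorrect reason and reach unsized hematomas, which could qualify under either list.

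Fourth, the EU figure belongs to another study. Its five hematomas came from events recorded as larger than 6 cm, a threshold found in neither MARVEL list. A different definition may explain 0/50, but Table 2 gives none.

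The CEC charter, the classification list used by the CEC and the table templates are not in these documents and might show which list was applied.

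**Conclusion.** The point holds and should be fixed. SAP 5.3 does not analyse the minor-complication endpoint that Protocol 8.3.1 defines: it drops the catch-all and excludes patients with a major complication. SAP 3 also keeps from adjudication some events that Protocol 9.5.1 sends there, on a rationale that fails under the catch-all. One benchmark the SAP commits to using contradicts the protocol's account of the same study.

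On equal denominator, window and onset dates, the SAP 5.3 rate is equal to or below the protocol rate. The size is not determinable. Only the no-major part can be bounded: 0 up to 10 to 21 patients at Table 2 VARC-2 major rates, or up to about 5 to 46 across the MANTA rows of Table 3, all with N = 500 assumed.

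Two stronger readings are not supported. A reader might infer that the narrower definition would change the statement reported against the literature; that is possible but not shown. A reader might also infer a deliberate narrowing, because the SAP was drafted after enrollment closed. The documents say nothing of motive, and the five-element list already stands in the protocol synopsis. The wording conflicts are certain and their effect is not. The endpoint is descriptive, and Protocol Sections 5 and 8.3.1 call it secondary.

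**What to change.** 1. In SAP 5.3, report the minor-complication rate regardless of major complications, as in Protocol 8.3.1, with the minor-without-major version as a second labelled row.
2. Show the rate with and without the catch-all. State which is the protocol endpoint and which is compared with VARC-2 literature rates. Bring the synopsis, Protocol Section 4, SAP 5.3 and SAP Appendix 1 into line.
3. State how access-site relatedness is decided for the catch-all, since the CEC fields in SAP 3 cover only device and procedure relatedness. Note that the catch-all needs a definite or probable rating, whereas SAP 5.6 also treats possible and unknown as related.
4. Align SAP 3 with Protocol 9.5.1 by sending the withheld MANTA-leg events rated at least possibly device-related to the CEC, including hematomas of unrecorded size. Otherwise report them as a labelled, unadjudicated sensitivity count, with unsized hematomas separate, and disclose the departure. Correct the stated rationale either way.
5. In SAP Table 2, give the definition behind 0/50 and reconcile it with the 5/50 in Protocol 1.4.

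The cost is wording in SAP Sections 3, 5 and 5.3 and Appendix 1, a clarification of the protocol synopsis, a few table rows from adverse event data already collected, and some added CEC review. That review grows if access-site relatedness has to be judged afresh. The downside for the sponsor is a possibly less favourable minor-complication rate.
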